2. When DSW reaches 100% re-epithelialization by Day 14, a re-confirmation of wound closure will be performed on Day 28.										

3. Day 42 visit is only for patients whose DSWs do not reach to 100% re-epithelialization on Day 14 but heal on Day 28 as a re-confirmation.
4. For patients whose visit 8 (Day 42) is scheduled, these visits will be arranged at 90, 180, 270 and 360 days after visit 8 (Day 42); otherwise, these follow-ups will be planned at 90, 180, 270 and 360 days after visit 7 (Day 28). These long-term follow-ups should be scheduled even if 100% re-epithelialization is not observed on Day 28 or Day 42.
5. For treatment group: TWB-103+TegadermTM. For the control group: placebo+TegadermTM. The application will be discontinued when the 100% re-epithelialization of DSW is observed by the investigator.
6. The size of TegadermTM to be used for each patient will be determined by the investigator based on the size of DSW. Whenever TegadermTM falls off from DSW site, new TegadermTM should be applied immediately. If necessary, drainage is allowed, but re-application of TWB-103 or placebo is not necessary in this case.
7. TegadermTM is applied to the wound site after the investigator has finished the wound assessment if the DSW has not reached 100% re-epithelialization, regardless the original group assignment.
8. TegadermTM is dispensed to the patient regardless of the condition of DSWs. Patients are advised to apply TegadermTM to DSW site if the wound open remains or reappears, and to re-apply new TegadermTM every 2~3 days till next visit or wound closure. The amount of TegadermTM dispensed should be adequate for patient's use till next visit.
9. Unused TegadermTM is returned to the study site if TegadermTM is dispensed to the patient at the previous visit. Re-dispensing of unused TegadermTM to the same patient is allowed when the primary package of TegadermTM remains intact.
10. The patient will receive the application of TegadermTM on site for protection of wound site and/or start with other treatment recommended by the investigator if DSW does not reach 100% re-epithelialization by Day 28.

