2.2 Endpoints

2.2.1. Primary endpoints

The primary endpoint for this study is:

Phase I

Safety:

Incidence of treatment-related AEs and SAEs (including infections and bleeding)

Phase I+II

Efficacy:

The healing time from DSW creation to the first 100% re-epithelialization with confirmation for at least 10 days apart, assessed by the investigator

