4. STUDY DESIGN

This study will be designed in a Phase I/II randomized, double-blind, additional evaluator-blind, placebo-controlled, multi-center, multi-nation (Taiwan and Japan), parallel manner. This study is to evaluate the safety and efficacy of the TWB-103 in adult patients with split-thickness skin graft donor site wounds (DSW). The study will recruit 30 evaluable patients, approximately up to 36 patients to be recruited to complete a total of 30 evaluable patients. Eligible patients will be randomly assigned in 1:1 ratio to one of the following groups:

Treatment Group:

TWB-103 add-on TegadermTM till 100% re-epithelialization or up to 10 days, whichever comes first, followed by TegadermTM alone application from Day 10 to Day 14 if failing to achieve 100% re-epithelialization by Day 10. If 100% re-epithelialization is not observed on Day 14 (the end of treatment), patients will have application of TegadermTM up to Day 28.

Control Group:

Placebo+TegadermTM till 100% re-epithelialization or up to 10 days, whichever comes first, followed by TegadermTM alone application from Day 10 to Day 14 if failing to achieve 100% re-epithelialization by Day 10. If 100% re-epithelialization is not observed on Day 14 (the end of treatment), patients will have application of TegadermTM up to Day 28.

Note:

1. TegadermTM will be renewed at each visit between Visit 3 (Day 3) to Visit 7 (Day 28) if 100% re-epithelialization is not observed. Whenever TegadermTM falls off from DSW site, new TegadermTM should be applied immediately. If necessary, drainage is allowed, but re-application of TWB-103 or placebo is not necessary in this case.

2. If the first 100% re-epithelialization is observed on Day 28, patients will be scheduled Day 42 follow-up and dispensed with Tegaderm™.
3. If the first 100% re-epithelialization is not observed on Day 28, patients will receive the application of Tegaderm™ on site for protection of wound site and/or have other appropriate treatment at the investigator's discretion. The DSWs will be followed till 100% re-epithelialization.
4. To prevent the itchiness and skin reaction caused by the long-term usage of Tegaderm™, Vaseline Gauze or Non-Stick Gauze such as silastic foam dressings can be used on and after Day 14 at the investigator's discretion.

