All subjects are scheduled to attend a follow-up visit on Day 28 to evaluate the status of the target wound and then enter a 360-day follow-up phase. If the complete wound closure occurs by Day 14, the re-confirmation of wound closure should be performed on Day 28 follow-up. In the case that complete wound closure occurs at some point between Day 14 and Day 28, an additional follow-up visit will be scheduled on Day 42 for the re-confirmation before subject enters the 360-day follow-up phase. If the complete wound closure is not observed on Day 28, patients will have other appropriate treatment at the investigator's discretion. The DSWs will be followed till 100% re-epithelialization.

During the 360-day follow-up, four follow-up visits will be scheduled at 90 ± 14 days, 180 ± 14 days, 270 ± 14 days and 360 ± 14 days following the subject's Day 28 visit (if no

Day 42 visit) or Day 42 visit. In total, 5~6 follow-up visits will be scheduled in this study for all randomized subjects.

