6.11 Wound assessment

The wound assessment will be measured at all scheduled visits except the Screening Visit.

From Visit 2 (Day 0) to Visit 8 (Day 42), the investigator will determine the end of treatment based on the healing progress. Wound healing will be assessed based on the wound observation by the investigator and an additional evaluator. An additional evaluator who is not aware of the treatment given will evaluate based on photos of the wound. The additional evaluator will receive photos of the wound from CRO and will return the assessment to CRO. A second additional evaluator, who is also blinded, will

be requested when the discrepancy occurs between investigator and the first additional evaluator in the determination of 100% re-epithelialization.

The photos of wound will be taken under the following guidelines.

- (a) Cameras and rulers with the same brand and model will be used throughout the study.
- (b) The study staff who are trained will be in charge of taking photos following the guidelines for each study center.
- (c) Two different photos will be taken for each wound at each visit: one for the calculation of wound healing and the other as the reference of the wound location relative to the body part.
- (d) The wound area shown in the photo specific for calculation purpose, along with the provided ruler, should have sufficient size and quality for evaluation.
- (e) Images will be processed by the software, Image J.
- (f) The investigator and evaluator(s) will select the boundary of said wound in the photo manually and by the wand tool in Image J.
- (g) Calculate the wound size by Image J based on the area selected.
- (h) The healing percentage of wounds will be calculated by the ratio of healing area and original area (Day 0).

Complete wound closure is defined as skin 100% re-epithelialization without drainage or dressing requirements. Wound closure should be re-confirmed on Day 28 when the complete wound closure occurs by Day 14, or on Day 42 in the case that complete wound closure occurs at some point between Day 14 and Day 28.

During the 360 days of follow-up (Visit 9~12), recording of 100% re-epithelialization and the area of target wound are not required. Instead, potential long-term adverse

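### The Day 42 confirming visit is triggered by 100% re-epithelialization in some sections and by wound closure in others, so a few Day 28 healers may be events or censored depending on the section followed

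*Combined protocol and SAP*

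**What the plan says.** Section 2.2.1 gives the primary efficacy endpoint as "The healing time from DSW creation to the first 100% re-epithelialization with confirmation for at least 10 days apart, assessed by the investigator". Section 6.11 defines a second state: "Complete wound closure is defined as skin 100% re-epithelialization without drainage or dressing requirements". Section 2.2.2 gives that state its own endpoint, the healing rates in secondary efficacy endpoint 2.

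The rules for confirmation and the Day 42 visit use both terms:

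- Section 4 Note 2, repeated in the synopsis (Patient Assignment) and in Sections 4.1 and 5.2: "If the first 100% re-epithelialization is observed on Day 28, patients will be scheduled Day 42 follow-up".
- Section 7.5.2 and note 2 of the synopsis visit list: Day 42 takes place only if wound closure was incomplete by Day 14 but is seen on Day 28.
- The follow-up paragraph of Section 4: if "complete wound closure occurs at some point between Day 14 and Day 28, an additional follow-up visit will be scheduled on Day 42". The synopsis (Study Design) and Section 6.11 use the same trigger. For earlier healing, Section 6.11 adds "Wound closure should be re-confirmed on Day 28 when the complete wound closure occurs by Day 14".
- Schedule of Assessments, note 2: "When DSW reaches 100% re-epithelialization by Day 14, a re-confirmation of wound closure will be performed on Day 28".
- Schedule of Assessments, note 3, repeated under the Study Schema: "Day 42 visit is only for patients whose DSWs do not reach to 100% re-epithelialization on Day 14 but heal on Day 28".

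Section 10.2.2 and the synopsis (Statistical Analysis) censor a wound seen healed by Day 28 but not confirmed, at the last visit up to Day 28. Neither says whether the confirming visit must show 100% re-epithelialization or complete wound closure.

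**The concern.** An event that needs confirmation depends on the visit that can confirm it. For a wound first healed on Day 28, that visit is Day 42. If one section schedules it by the endpoint state and another by a stricter state, two sites can follow the protocol faithfully and code the same wound differently in the primary log-rank test. A visit that was never scheduled leaves no data, so the analyst cannot choose the intended definition afterwards. With 15 evaluable patients per arm, there is little room for events that turn on which page was read.

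**Working it through.** The plan gives no event count or power calculation, so there is no figure to reproduce. The check compares the texts and then sizes the affected group.

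**Step 1: the wound on which the rules disagree.** Take a wound that is not re-epithelialized on Day 14, is 100% re-epithelialized for the first time on Day 28, and still drains or is judged to need a dressing that day.

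| Text followed | Day 42 visit? | Status in the primary analysis |
|---|---|---|
| Note 2 (Sections 4, 4.1, 5.2; synopsis) | Yes | Event at Day 28 if confirmed on Day 42 |
| Section 7.5.2; synopsis visit list note 2 | No, since closure is not seen on Day 28 | Censored at Day 28 under Section 10.2.2 |
| Section 4 follow-up paragraph; Section 6.11; synopsis Study Design | Not provided for | Censored at Day 28 unless another rule supplies the visit |

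The second row reads wound closure in the sense of the defined term. The recorded time is Day 28 in every row; only the event indicator changes.

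**Step 2: can a later visit supply the confirmation?** The next scheduled visits are Visits 9 to 12, and Section 6.11 does not require 100% re-epithelialization to be recorded there. Follow-up beyond Day 28 runs until 100% re-epithelialization, which this wound has already reached. Only an unscheduled visit could confirm it, and those depend on a need for medical attention (Section 4.3.4).

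**Step 3: wounds healed by Day 14.** All patients attend Day 28 and have a wound assessment there (Sections 4 and 7.5.1), so no visit is lost under either wording. What is open is which state counts as confirmation, and that can be settled at analysis.

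**Step 4: size.** From the documents: about 36 recruited, 30 evaluable. Assumed: one third first heal at Day 28; 5% to 20% of those are re-epithelialized but not closed.

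- First healed at Day 28: 36 / 3 = 12
- Status at issue: 0.05 × 12 = 0.6 to 0.20 × 12 = 2.4, or about 1 to 2 patients
- Standard error of the log hazard ratio, approximated as 2/√events:
  - 30 events: 2/√30 = 0.365
  - 28 events: 2/√28 = 0.378
  - Increase: √(30/28) − 1 = 3.5%

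The 30 events take one per evaluable patient, for illustration.

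**Step 5: sensitivity of the test to single wounds.** Assume 15 per arm, all healed, with counts at Days 10/14/28 of 5/7/3 (treated) and 2/6/7 (control). The log-rank p-value is 0.091. Recoding one treated Day 28 healer as censored gives 0.219; recoding one control Day 28 healer instead gives 0.072. The counts are invented, so this shows sensitivity only and predicts nothing about the trial.

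**The case against.** The strongest reply is that the authors used the two terms interchangeably. Schedule note 2 puts both in one sentence. Section 4 also describes the path of a wound unhealed on Day 28 once by closure and once, in Note 3, by re-epithelialization. In addition, the follow-up paragraph of Section 4 and Section 6.11 do not forbid a Day 42 visit for the wound in question. They are silent on it, while Note 2 schedules it in four places. The dressing rules narrow the gap further: dressings are applied or renewed at visits only if 100% re-epithelialization is not seen (Section 4 Note 1, Schedule note 7, Section 7.5.1), and at home only if the wound is open or reopens (Section 6.15). A wound that is re-epithelialized yet needs a dressing should be uncommon, which leaves mainly wounds that still drain.

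Most of this stands, and it limits the size of the problem. It does not remove the conflict, because the protocol defines closure explicitly, gives it a separate endpoint, and uses the word only in Section 7.5.2 and the synopsis visit list. A site cannot know that the definition was meant to be ignored.

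A reader might infer more than the documents support:

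- **Healing by Day 14 turning into censoring at Day 28.** This would require confirmation to mean closure, which Section 10.2.2 does not say. The Day 28 assessment takes place in any case.
- **A wound first seen healed at an unscheduled visit between Day 14 and Day 28 losing its Day 42 visit.** Section 7.5.2, the synopsis visit list and Schedule note 3 require closure or healing on Day 28, not first seen that day. Note 2 says first but excludes nobody.
- **A rate of 5% to 20% applied to all 36 patients.** This gives 1.8 to 7.2 patients and, at 24 events, a standard error of 0.408 (+12%). The conflict concerns only wounds first healed at Day 28, so that range is too wide.

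**Conclusion.** The concern holds in a narrow form. For a wound first 100% re-epithelialized on Day 28 but not closed, the current text both schedules and withholds the only planned confirming visit. Section 10.2.2 then makes the wound an event or a censored observation accordingly. Section 10.2.2 also leaves the confirming state undefined. For healing by Day 14 that omission can be repaired at analysis; for the Day 28 group it cannot be repaired from scheduled data.

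On the stated assumptions about 1 to 2 patients are affected, with a loss of precision near 3.5%. The documents give neither the share first healing at Day 28 nor how often re-epithelialization and closure differ, so the true number could be zero. The point is still worth correcting: it concerns how the primary event is ascertained, the arms are small, and the correction costs almost nothing.

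**What to change.** Reconcile the passages on the state named in the primary endpoint:

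1. Use 100% re-epithelialization for the event, its confirmation and the Day 28 and Day 42 triggers. The texts to change are the synopsis (Study Design; Study Visits notes 1 and 2), Schedule of Assessments notes 2 and 3 with the matching Study Schema note, the follow-up paragraph of Section 4, Section 6.11 and Section 7.5.2.
2. State in Section 10.2.2 and the synopsis (Statistical Analysis) that the confirming visit must show 100% re-epithelialization.
3. Word the Day 42 trigger identically everywhere, including each copy of Note 2: first 100% re-epithelialization recorded after Visit 6, up to and including Visit 7.
4. Keep complete wound closure for secondary efficacy endpoint 2 only.

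The cost is a wording amendment and possibly a few extra Day 42 visits.

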6.12 Pain assessment

The pain assessment will be measured by employing short-form McGill pain questionnaire and will be performed at all scheduled visits, except Visit 2 (Day 0), starting from the Screening visit. Patients should evaluate pain level at the (future) DSW site.

6.13 Exit of Study

The patient should complete the last follow-up (Visit 12) before exiting from the study, regardless of the treatment groups and the wound healing outcome.

6.14 Panel reactive antibodies (PRA) test

All patients (Phase I + Phase II) will be tested with Class I HLA on Day 0 and Day 28. The same testing kit should be employed for all labs. For Visit 2, the PRA test conducted within 7 days prior to Day 0 is acceptable.

Note: HLA = Human leukocyte antigen

6.15 Tegaderm™ dispensing and return

The size of Tegaderm™ to be used for each patient will be determined by the investigator based on the size of DSW. Sufficient amount of Tegaderm™ will be dispensed to patients. The amount of Tegaderm™ dispensed should be adequate for patient's use till next visit. Patients are advised to apply Tegaderm™ to DSW site if the wound open remains or reappears, and to re-apply new Tegaderm™ every 2~3

days till next visit or wound closure. Whenever Tegaderm™ falls off from DSW site, new Tegaderm™ should be applied immediately. Unused Tegaderm™ will be returned to the clinical site at the next visit. Re-dispensing of unused Tegaderm™ to the same patient is allowed when the primary package of Tegaderm™ remains intact. Tegaderm™ will be dispensed to patients from Visit 2 (Day 0) to Visit 7 (Day 28). However, at Visit 7 (Day 28), Tegaderm™ is dispensed only when Visit 8 (Day 42) is scheduled. To prevent the itchiness and skin reaction caused by the long-term usage of Tegaderm™, Vaseline Gauze or Non-Stick Gauze such as silastic foam dressings can be used on and after Day 14 at the investigator's discretion.

7. STUDY SCHEUDLE

7.1 Screening visit

(Visit 1: within 2 weeks prior to DSW creation)

- Explain the nature of the study and have patients to read and sign an Informed Consent Form
- Assign patient screening number
- Obtain demographic characteristics
- Obtain medical history
- Obtain vital signs
- Perform physical examinations
- Perform pregnancy test for applicable patients
- Obtain blood samples for hemogram and biochemical tests
- Screen patients for inclusion/exclusion criteria
- Pain questionnaire
- Record adverse events
- Record prior/concomitant treatments
- Randomization (before DSW creation but after all baseline procedures are completed and the subject has been deemed eligible for the study)

7.2 Administration Visit

(Visit 2: Day 0)

Before DSW creation

- Perform physical examinations
- Obtain vital signs
- Obtain blood samples for hemogram and biochemical tests (the hematologic and biochemical tests conducted within 7 days prior to Day 0 are acceptable)
- Obtain blood samples for PRA test (the PRA test conducted within 7 days prior to Day 0 is acceptable)

After DSW creation

- Wound assessment (including the thickness of DSW)
- Apply study medications (treatment group: TWB-103+ TegadermTM; control group: placebo+TegadermTM)
- Dispense TegadermTM to patients
- Record adverse events
- Record concomitant treatments

7.3 Evaluation Visits

7.3.1 Visit 3: Day 3 ± 1 day

- Perform physical examinations
- Obtain vital signs
- Obtain blood samples for hemogram and biochemical tests
- Pain questionnaire
- Wound assessment

- Apply study medications (if not 100% re-epithelialization. Treatment group:
TWB-103+ TegadermTM; control group: placebo+TegadermTM)
- Dispense TegadermTM to patients
- Return unused TegadermTM (if received at previous visit)
- Record adverse events
- Record concomitant treatments

7.3.2 Visit 4: Day 7 ± 1 day

- Perform physical examinations
- Obtain vital signs
- Obtain blood samples for hemogram and biochemical tests
- Pain questionnaire
- Wound assessment
- Apply study medications (if not 100% re-epithelialization. Treatment group:
TWB-103+ TegadermTM; control group: placebo+TegadermTM)
- Dispense TegadermTM to patients
- Return unused TegadermTM (if received at previous visit)
- Record adverse events
- Record concomitant treatments

7.3.3 Visit 5: Day 10 ± 1 day

- Perform physical examinations
- Obtain vital signs

- Obtain blood samples for hemogram and biochemical tests
- Pain questionnaire
- Wound assessment
- Apply Tegaderm™ (if not 100% re-epithelialization, for both treatment and control group)
- Dispense Tegaderm™ to patients
- Return unused Tegaderm™
- Record adverse events
- Record concomitant treatments

7.4 The end of treatment visit

(Visit 6: Day 14 days ± 2 days)

- Perform physical examinations
- Obtain vital signs
- Obtain blood samples for hemogram and biochemical tests
- Pain questionnaire
- Wound assessment
- Apply Tegaderm™, Vaseline Gauze or Non-Stick Gauze (if not 100% re-epithelialization, for both treatment and control group)
- Dispense Tegaderm™, Vaseline Gauze or Non-Stick Gauze to patients
- Return unused Tegaderm™
- Record adverse events

- Record concomitant treatments

7.5 Follow-up visits

7.5.1 Visit 7: Day 28 ± 3 days

- Perform physical examinations
- Obtain vital signs
- Obtain blood samples for hemogram and biochemical tests
- Obtain blood samples for PRA test
- Pain questionnaire
- Wound assessment
- Apply Tegaderm™, Vaseline Gauze or Non-Stick Gauze (if not 100% re-epithelialization, for both treatment and control group)
- Dispense Tegaderm™, Vaseline Gauze or Non-Stick Gauze to patients (only for patients who have Day 42 Visit)
- Return unused Tegaderm™, Vaseline Gauze or Non-Stick Gauze
- Record adverse events
- Record concomitant treatments

7.5.2 Visit 8: Day 42 ± 3 days

(Only scheduled when the wound closure is not completed by Day14 but is observed on Day 28)

- Perform physical examinations
- Obtain vital signs

- Obtain blood samples for hemogram and biochemical tests
- Pain questionnaire
- Wound assessment
- Return unused Tegaderm™, Vaseline Gauze or Non-Stick Gauze
- Record adverse events
- Record concomitant treatments

7.5.3 Visit 9~12 (90, 180, 270, 360 days ± 14 days after Visit 7 (if no visit 8) or Visit 8)

- Perform physical examinations
- Obtain vital signs
- Pain questionnaire
- Wound assessment (scar assessment, skin texture and any altered sensations, see details in section 6.11)
- Record adverse events (only TWB-103/placebo-relative and DSWs-relative adverse events will be recorded)
- Exit of study (Visit 12)

8. ADVERSE EVENTS

8.1 Definitions

- Adverse Event (AE):

An AE is any untoward medical occurrence in a patient or clinical investigation participant administered a study medication and that does not necessarily have a causal relationship with this treatment. An AE can therefore be any unfavorable and unintended sign, symptom, or disease temporally associated with the use of a study medication, whether or not related to the study medication. Laboratory abnormalities should not be recorded as AEs unless determined to be clinically significant by the Investigator.

- Expected AE:

Expected AE are defined as any event, the specificity or severity of which is consistent with the current investigator brochure.

- Unexpected AE:

Unexpected AE is defined as any event, the specificity or severity of which is not consistent with the current investigator brochure. "Unexpected", as used in this definition, refers to an adverse drug experience that has not been previously observed (e.g., included in the investigator brochure) rather than from the perspective of such experience not being anticipated from the pharmacological properties of the pharmaceutical product.

- Serious Adverse Event (SAE):

Serious Adverse Event (SAE): A Serious Adverse Event is defined as an AE meeting one of the following conditions:

- Death during the period of protocol defined surveillance
- Life Threatening Event (defined as a participant at immediate risk of death at the time of the event)
- An event requiring inpatient hospitalization or prolongation of existing hospitalization during the period of protocol defined surveillance
- Results in congenital anomaly or birth defect
- Results in a persistent or significant disability/incapacity
- Based upon appropriate medical judgment, the event may jeopardize the participant and may require medical or surgical intervention to prevent one of the outcomes listed above.

